IRB	Institutional Review Board
IUD	Intra Uterine Device
LNGFR	Low-affinity nerve growth factor receptor

LPLV	Last Patient Last Visit
MedDRA	Medical Dictionary for regulatory activities
mcg/mL	micrograms/millilitre
NEI	National Eye Institute
NIMP	Non-Investigational Medicinal Product
NGF	Nerve Growth Factor
NK	Neurotrophic Keratitis
PI	Principal Investigator
PID	Patient Identification number
PP	Per Protocol Population
PT	Preferred Term
p75NTR	p75 Neurotrophin Receptor
rhNGF	recombinant human Nerve Growth Factor
RP	Retinitis Pigmentosa
SAE	Serious Adverse Event
SAF	Safety population
SANDE	Symptom Assessment iN Dry Eye
SAP	Statistical Analysis Plan
SD	Standard Deviation
SLE	Slit-Lamp Examination
SOC	System Organ Class
SUSAR	Suspected Unexpected Serious Adverse Reaction
TEAE	Treatment Emergent Adverse Event
TFBUT	Tear Film Break-Up Time
TID	Ter in die (thrice a day)
TrkA	Tropomyosin receptor kinase A
USA	United States of America
Vs	Versus
§	Section

1. STUDY SYNOPSIS

CLINICAL STUDY SYNOPSIS:	
Study Number	NGF0121
Title of Study	A 4-week, Phase III, multicenter, double-masked, vehicle-controlled clinical study to evaluate safety and efficacy of Oxervate® (cenegermin) 20 mcg/mL ophthalmic solution versus vehicle, in patients with severe Sjogren's dry eye disease (PROTEGO-1 study)
Study Name	PROTEGO-1
IND N°	115892
EUDRACT:	2021-003346-21
Study Centers (Country)	Approximately 10 study sites in Europe and USA
Development Phase	Phase III
Objective	The primary objective of this study is to assess the efficacy and safety of cenegermin ophthalmic solution at 20 mcg/mL concentration administered three times daily for 4 weeks in patients with severe Sjogren's dry eye disease.
Study Design and Methodology	This is a phase III, multicenter, double-masked, parallel-arm, vehicle-controlled trial.
Number of Patients	Randomization 1:1 of 90 patients to cenegermin ophthalmic solution 20 mcg/mL TID or vehicle ophthalmic solution TID for 4 weeks. Assuming a dropout rate of 10%, up to 100 patients are expected to be enrolled.
Main Inclusion criteria	

 1. Male or female aged \geq 18 years 2. Patients with a confirmed diagnosis of Sjogren's syndrome or other autoimmune disease known to induce Sjogren's Dry Eye Disease (DED). 3. Patients with severe Sjogren's dry eye disease characterized by the following clinical features: 
 a. Corneal and/or conjunctival staining with fluorescein using National Eye Institute (NEI) grading system ≥ 3 b. SANDE questionnaire global score > 25 mm c. Schirmer test I (without anaesthesia) $\geq 2 \leq 5$ mm/5min 4. The same eye (eligible eye) must fulfill all the above criteria 5. Diagnosis of severe Sjogren's dry eye disease at least 3 months before enrollment (current use or recommended use of artificial tears for the treatment of Sjogren's related Dry Eye) 6. Best corrected distance visual acuity (BCDVA) score of ≥ 0.1 decimal units (20/200 Snellen value) in each eye at the time of study enrolment 7. If a female of childbearing potential, have a negative urine pregnancy test and use a highly effective method to avoid pregnancy for the duration of the trial and 30 days after the 	

study treatment period. Males of reproductive potential should use effective contraception during treatment and 30 days after the study treatment period

8. Only patients who satisfy all Informed Consent requirements may be included in the study. The patient and/or his/her legal representative must read, sign and date the Informed Consent document before any study-related procedures are performed. The Informed Consent Form signed by patients and/or legal representative must have been approved by the IRB/IEC for the current study
9. Patients must have the ability and willingness to comply with study procedures.

Main exclusion criteria

1. Inability to speak and understand the local language sufficiently to understand the nature of the study, to provide written informed consent, and to allow the completion of all study assessments
2. Evidence of an active ocular infection, in either eye
3. Presence of any other ocular disorder or condition requiring topical medication during the entire duration of study in either eye
4. History of severe systemic allergy or of ocular allergy (including seasonal conjunctivitis) or chronic conjunctivitis and/or keratitis other than dry eye
5. Intraocular inflammation defined as Tyndall score >0
6. History of malignancy in the last 5 years
7. Systemic disease not stabilized within 1 month before Screening Visit (e.g. diabetes with glycemia out of range, thyroid malfunction) or judged by the investigator to be incompatible with the study (e.g. current systemic infections) or with a condition incompatible with the frequent assessment required by the study
8. Patient with a history of serious adverse reaction or significant hypersensitivity to any drug or chemically related compounds or clinically significant allergy to drugs, foods, amide local anesthetics or other materials including commercial artificial tears (in the opinion of the investigator)
9. Females of childbearing potential (those who are not surgically sterilized or post-menopausal for at least 1 year) are excluded from participation in the study if they meet any one of the following conditions:
 - a. are currently pregnant or,
 - b. have a positive result at the urine pregnancy test (Baseline/Day 1) or,
 - c. intend to become pregnant during the study treatment period or,
 - d. are breast-feeding or,
 - e. are not willing to use highly effective birth control measures, such as: combined (estrogen and progesterone containing) hormonal contraceptives associated with inhibition of ovulation (oral, intravaginal, transdermal), progestogen-only hormonal contraception associated with inhibition of ovulation (oral, implantable, injectable), intrauterine device (IUD), intrauterine hormone-releasing system (IUS), bilateral tubal occlusion, vasectomised partner, sexual abstinence during the entire course of and 30 days after the study treatment period

- 10.** Any concurrent medical condition, that in the judgment of the PI, might interfere with the conduct of the study, confound the interpretation of the study results, or endanger the patient's well-being
- 11.** Use of topical cyclosporine, or topical ophthalmic treatments of the same class, within 14 days of screening visit (day -8).
- 12.** Use of topical corticosteroids, lifitegrast, autologous serum tears in either eye during the study (previous use not an exclusion criteria but must be discontinued at the screening visit)
- 13.** Contact lenses, TrueTear device, moisture goggles, sutureless amniotic membrane or punctum plug use during the study (previous use not an exclusion criteria but must be discontinued at the screening visit)
- 14.** History of drug addiction or alcohol abuse within the last year
- 15.** Any prior ocular surgery (including refractive, palpebral and cataract surgery) if within 90 days before the screening visit
- 16.** Participation in a clinical trial with a new active substance during the past 3 months prior to screening
- 17.** Participation in another clinical trial study at the same time as the present study

Test/Reference Product, Dosage and Mode of Administration	
Oxervate®, an ophthalmic solution containing cenegermin 20 mcg/mL, which is a recombinant human Nerve Growth Factor (rhNGF); reference product is vehicle. Test and reference will be instilled in both eyes according to the following scheme:
 
Group 1: one drop of cenegermin 20 mcg/mL will be instilled in both eyes three times daily (every 6 hours, e.g. 7:00 am, 01:00 pm; 07:00 pm).
 
Group 2: vehicle eye one drop will be instilled in both eyes three times daily (every 6 hours, e.g. 7:00 am, 01:00 pm; 07:00 pm).
 
The IMP will be provided in a monthly box containing 28 daily vials. Together with the IMP monthly box, patients will be provided with a sufficient number of pipettes and adaptors for the administration of the IMP.

Duration of Study	
Patients will be evaluated at screening visit (day -8), baseline (day 1+2), week 2 (day 14±2), week 4 (day 28±2) or early exit, week 8 (day 56±2), week 12 (day 84±4), and week 16 (day 112±7) of follow-up. Safety evaluations will also be continued in follow-up until week 24 (day 168 ±7)
 
Screening Visit (day -8): all procedures for assessment of eligibility will be performed.

	
Wash-out period (from day -8 to baseline): 8 (+2) days with no further treatment except commercially available preservative free artificial tears if strictly needed, provided by the Sponsor. The use of artificial tears will be tracked in the patient's diary.
 
Treatment: eligible patients will be randomized 1:1 and treated for 4 weeks with either cенегермин ophthalmic solution 20 mcg/mL or vehicle. Only the experimental IMP is allowed during the treatment period however, if strictly needed, the patient may use commercially available preservative free artificial tears provided by the Sponsor. The use of artificial tears will be tracked in the patient's diary.
 
Follow up: Initially 8 weeks (from week 5 to week 12) post treatment with no further topical ocular treatment except commercially available preservative-free artificial tears provided by the Sponsor administered three times daily. Furthermore, the patient can administer additional artificial tear eye drops provided by the Sponsor only if strictly needed, and must document in the patient's diary the number of additional drops administered for each eye. Patients will then be followed up for efficacy and safety endpoints until week 16 and for safety endpoints until week 24. During the follow up period (from week 13 to week 24) other topical treatments will be allowed at discretion of the treating physician. Such treatments will be recorded by the investigators.
 
Patients can continue any systemic treatment as required to control their autoimmune disease throughout the study; any change in systemic treatments must be recorded by the investigators.
 
Maximum total study duration: 112±7 days for efficacy evaluations plus an additional 56±7 days for safety evaluations.

Study population	Patients with severe Sjogren's dry eye disease will be included. A total of 100 patients will be enrolled assuming a 10% drop out rate to yield 90 eligible patients.
Co- Primary Efficacy Endpoint	
 • Schirmer I test (without anesthesia) >10mm/5min at week 4 in the eligible eye. • Change from baseline in Symptoms questionnaire (SANDE) global score at week 12.

Secondary Efficacy Endpoints	
 • Change from baseline in Schirmer I test (without anesthesia) [Time frame: week 4, 8, 12 and 16]; • Change from baseline in Cornea and conjunctiva vital staining with fluorescein (National Eye Institute [NEI] scales) [Time frame: week 4, 8, 12 and 16]; • Change from baseline in Tear Film Break-Up Time (TFBUT) [Time frame: week 4, 8, 12 and 16]; • Change from baseline in Symptoms questionnaire (SANDE) scores for severity and frequency [Time frame: week 8, 12 and 16]; • Number of patients experienced worsening in symptom scores (SANDE) and/or NEI score $\geq 50\%$ assessed at week 4; • Quality of life (IDEEL) questionnaire [Time frame: week 4, 8, 12 and 16].
Exploratory Endpoints	
Safety Endpoint	
 • Incidence and frequency of Adverse Events (AEs) and Treatment-emergent adverse events (TEAEs), assessed throughout the study.

Statistical Methods	
The sample size of the study is calculated based on results from previous studies. Expecting a difference of 30% in Schirmer I rate of responders (defined as patients reaching a value >10mm/5min) at Week 4 and 15 points in Global SANDE score improvement at Week 12, a total sample size of 90 evaluable patients (100 pts considering 10% drop-out rate) allows to achieve an overall power of 90% to show superiority of cenegegermin ophthalmic solution vs vehicle in terms of both co-primary endpoints, considering a one-sided alpha of 0.025.
 
Summary statistics are defined for quantitative variables (number of observations, mean, standard deviation, median, minimum and maximum) and qualitative variables (number and percentage per category). If appropriate, confidence intervals around the mean or the proportions will be presented.
 
The proportion of patients reaching a value of Schirmer I test (without anesthesia) >10mm/5min at week 4 will be analyzed by means of logistic regression. The change from baseline in SANDE global score at week 12 will be analyzed by means of an adjusted ANCOVA procedure.
 
If the primary analysis of primary endpoint leads to rejection of the null hypotheses, key secondary endpoints will be tested in a conditional sequential manner to show superiority of cenegegermin versus placebo vehicle according to the pre-defined ranking sequence. Independently of the results on primary endpoints, all secondary endpoints will be analysed at each available time point by means of descriptive statistics and by appropriate parametric tests. Data record in the questionnaires of quality of life will be presented with appropriate descriptive statistics and processed with appropriate inferential test. Change from baseline value and shift tables versus baseline may be summarized for all available post-baseline visits.
 
CCI [REDACTED] will be descriptively summarized at each available time point. Any statistical testing will be descriptive in nature. Correlation between sign and symptom scores will be assessed.
 
AEs will be coded by System Organ Class (SOC) and Preferred Term (PT), using the Medical Dictionary for Regulatory Activities (MedDRA). Individual AEs will be listed in patient data listings. TEAEs will be presented in terms of the number of AEs and incidence by treatment, seriousness,

----------------------------	--

	
relationship to treatment, severity, and study period (treatment or follow-up).
 
The Safety (SAF) and the Full Analysis Set (FAS) population will consist of all patients who will be randomized and received at least one dose of the investigational product. Safety population will be analyzed according to the actual treatment received; Full Analysis Set population will be analyzed according to ITT principle, i.e. by treatment allocation. The Per Protocol (PP) population will consist of all patients in the FAS population who do not have Major Protocol Deviations. Primary and secondary efficacy analyses will be conducted on the FAS population while SAF and PP populations will be used for safety and sensitivity analyses, respectively.
 
The Statistical Analysis Plan (SAP) will be issued before database lock with more technical and detailed elaboration of the principal features of statistical analyses. Any deviation from the original statistical plan will be described in the Clinical Study Report.

--	---

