6.1. SCREENING AND RANDOMIZATION VISITS

During the screening visit (day -8) all procedures for will be performed. From the day of screening the patients will stop any kind of further ophthalmic treatment, until all of the final study evaluations have been completed, except preservative free artificial tears (wash out period from day -8 to baseline, Day 1 +2). The wash out period should not be less than 8 days and more than 10 days.

At the end of the screening period, patients meeting the entry criteria for this study will be randomized 1:1 and treated for 4 weeks with either cenegeamin ophthalmic solution 20 mcg/mL TID or vehicle TID.

Slit lamp examination and the fluorescein staining (Corneal and/or Conjunctival staining with Fluorescein) will be performed at different time-points, as specified in the section 2 of “SCHEDULE OF EVALUATIONS” and procedure will be detailed on the informed consent form.

An independent Blinded Reading Center (RC) will also be used to assess the images collected at protocol-specified time points and sent to the RC as specified in the RC procedure manual.

The RC will provide instructions for the slit lamp photography and the fluorescein staining procedures.

	Day	Procedures/Assessments

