Screening visit	Day -8	
The following procedures will be performed (order below is mandatory):
 
 ➤ Explanation to the patient of study aims, procedures and possible risks ➤ Informed consent signature ➤ Screening number allocation ➤ Patient eligibility: Inclusion/exclusion criteria evaluation ➤ Pregnancy test for female patients of childbirth potential ➤ Demographic data ➤ Ocular and systemic medical history ➤ Previous ocular and systemic medications (prior to start the study) ➤ Ocular examination of both eyes, to be performed by the physician investigator: 
 • Assessment by SANDE questionnaire • Assessment by IDEEL questionnaire • Assessment of best corrected distance visual acuity (BCDVA) • External Ocular Examination • Schirmer test I (without anesthesia) • Slit-lamp examination (SLE) to assess the eyelid (Meibomian glands), eyelid (erythema), eyelid (edema), lashes, conjunctiva erythema, lens, iris, anterior chamber, corneal horizontal diameter • TFBUT • Ocular surface staining (NEI score - corneal and conjunctival fluorescein staining) • ➤ AE collection ➤ Preservative free artificial tears dispensation 
The Investigator will dispense to the patients the preservative free artificial tears (Blink® Tears or equivalent), provided by Sponsor, to be used only if strictly needed by the patient (the patient must follow the instruction in the product leaflet). The patients will be instructed to enter information of self-administration of Blink® Tears or equivalent (if the administration has been occur per eye) and AE occurrence into the diary.
 
The diary will be given from the PI or delegate during this visit.

At home	Day -8 – Day 1+2 (baseline)	
 ➤ Recording any unusual medical conditions - AE monitoring (diary) ➤ Artificial tears use during the wash-out period (diary) 
Data will be recorded by the patient on the patient's diary.

	Day	Procedures/Assessments

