9.4.3. Analysis of efficacy variables

9.4.3.1. Primary analyses

The following null hypothesis is defined on the first primary endpoint: the proportion of patients reaching a value of Schirmer I test (without anesthesia) >10mm/5min at week 4 in cenegegermin (rhNGF) is lower or equal than control:

$$H_{01}: T_{rhNGF} \leq T_{CONTROL}$$

$$H_{11}: T_{rhNGF} > T_{CONTROL}$$

where T_{rhNGF} and $T_{CONTROL}$ are the proportion of patients reaching a value of Schirmer I test (without anesthesia) $>10\text{mm}/5\text{min}$ at week 4 for cenegegermin and control groups, respectively. The null hypothesis H_{01} will be rejected if the associated primary analysis p-value will be lower than 0.025.

This primary endpoint will be analyzed by means of a logistic regression adjusting by pre-defined baseline factors (site, gender, age class, baseline Schirmer I test value) and a one-sided test will be used to test for differences between treatment groups.

Similarly, the following null hypothesis is defined on the co-primary endpoint: the change from baseline in the global SANDE score at week 12 in cenegegermin is lower or equal than control:

$$H_{02}: \mu_{rhNGF} \leq \mu_{CONTROL}$$

$$H_{12}: \mu_{rhNGF} > \mu_{CONTROL}$$

where μ_{rhNGF} and $\mu_{CONTROL}$ are the change from baseline in the global SANDE score at week 12 for cenegegermin and control groups, respectively. The null hypothesis H_{02} will be rejected if the associated primary analysis p-value will be lower than 0.025.

This coprimary endpoint will be analyzed by means of an ANCOVA model adjusting by pre-defined baseline factors (site, gender, age class, baseline global SANDE score) and a one-sided test will be used to test for differences between treatment groups.

Both null hypotheses H_{01} and H_{02} must be rejected in order to claim superiority of cenegegermin over control. Consequently, no multiplicity correction of type I error will be applied on primary endpoints analysis.

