4.5 Baseline

Baseline is defined as the last visit prior to and including date of the randomization visit (Visit 1). Unless otherwise specified, baseline values are defined as the measurements taken during this visit. In case of multiple measurements during baseline visit, the last assessment will be considered as baseline evaluation before start of treatment.

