If there are not enough retrieved dropouts for convergence of MI-RD regression model, a reference-based Multiple Imputation (MI) approach will be adopted to consider a missing not at random (MNAR) mechanism for missing data: imputation of values in the rhNGF arm (above step #2) will be done using the non-missing values from the control group (this approach will be referred as "Copy Reference"). This approach does not assume benefits for rhNGF in case of discontinuation and limits a post-discontinuation clinical effect to that of vehicle. The final decision on the use of the MI-RD vs Copy-Reference for this endpoint will be done at the time of the analysis and reported in the CSR.

Whether for MI-RD or Copy-Reference approach, the adjusted estimated treatment differences in proportions between cenegegermin and vehicle at week 4 will be displayed together with the corresponding two-side 95% confidence intervals and p-value.

10.1.2.2 Change from baseline in the global SANDE score at week 12

This co-primary endpoint will be analyzed by means of an Analysis of Covariance (ANCOVA) adjusting by pre-defined baseline factors (gender, age class, baseline global SANDE score as fixed effects and site as random effect) and a one-sided test will be used to test for differences between treatment groups. Rules for derivation of SANDE scores are reported in section 12.2.

For the imputation of missing data, a regression model will be created by including the baseline global SANDE score, gender, age class, and intermediate global SANDE scores up to week 12. Two hundred data sets will be generated, and the random seed number will be 37103939. MI will be implemented in the following steps:

1. Partial imputation assuming MAR will be carried out to impute intermittent (non-monotone) missing data of global SANDE score based on a multivariate joint Gaussian imputation model using the MCMC method. A separate imputation model will be used for each treatment arm. In case of non-convergence or non-estimability issues, a single imputation model will be considered (with treatment arm added as explanatory variable to the model). A total of 200 datasets will be created. These datasets will be utilized in Step #2.
2. The remaining monotone missing data will be imputed using a MI regression including the same explanatory variables of the previous step. According to MI-RD approach, only non-missing values from retrieve dropouts will be used to inform the regression model.

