<pre> PROC MI DATA= EFFICACY01 NIMPUTE=200 SEED=37103939 OUT=EFFICACY_MONO1; VAR BASVAL SANDE_W2 SANDE_W4 SANDE_W8 AVAL; MCMC CHAIN=SINGLE NBITER=200 NITER=100 IMPUTE=MONOTONE; WHERE TRT=1; RUN; PROC MI DATA=EFFICACY01 NIMPUTE=200 SEED=37103939 OUT=EFFICACY_MONO2; VAR BASVAL SANDE_W2 SANDE_W4 SANDE_W8 AVAL; MCMC CHAIN=SINGLE NBITER=200 NITER=100 IMPUTE=MONOTONE; WHERE TRT=2; RUN; DATA EFFICACY_MONO; SET EFFICACY_MONO1 EFFICACY_MONO2; RUN; </pre>	<pre> PROC MI DATA= EFFICACY01 NIMPUTE=200 SEED=37103939 OUT=EFFICACY_MONO; VAR BASVAL TRT SANDE_W2 SANDE_W4 SANDE_W8 AVAL; MCMC CHAIN=SINGLE NBITER=200 NITER=100 IMPUTE=MONOTONE; RUN; </pre>
<pre> PROC SORT; BY _IMPUTATION_ SUBJID; RUN; </pre>	
<pre> PROC MI DATA=EFFICACY_MONO SEED=200582 NIMPUTE=1 OUT=EFFICACY_IMP; BY _IMPUTATION_; CLASS TRT AGE SEX EOTSTT; MONOTONE REG(AVAL = TRT AGE SEX / DETAILS); MNAR MODEL(AVAL / MODELOBS= (EOTSTT='NOT COMPLETED')); VAR TRT AGE SEX BASVAL SANDE_W2 SANDE_W4 SANDE_W8 AVAL; RUN; </pre>	<pre> PROC MI DATA=EFFICACY_MONO SEED=200582 NIMPUTE=1 OUT=EFFICACY_IMP; BY _IMPUTATION_; CLASS TRT AGE SEX EOTSTT; MONOTONE REG(AVAL = TRT AGE SEX / DETAILS); MNAR MODEL(AVAL / MODELOBS= (TRT=2 /*Vehicle*/)); VAR TRT AGE SEX BASVAL SANDE_W2 SANDE_W4 SANDE_W8 AVAL; RUN; </pre>

Standard	Alternative code in case of no convergence
<pre>ODS OUTPUT DIFFS=DIFFS; ODS OUTPUT PARAMETERESTIMATES=ESTIMATES; PROC MIXED DATA=EFFICACY_IMP; BY _IMPUTATION_; CLASS TRT(REF="1") SEXC(REF="F") SITEID; MODEL AVAL=TRT AGE SEXC BASVAL /S; RANDOM INTERCEPT / SUBJECT=SITEID; LSMEANS TRT / CL DIFF; RUN; ODS OUTPUT PARAMETERESTIMATES=POOLED_ESTIMATES; PROC MIANALYZE PARMS = ESTIMATES ; CLASS TRT SEXC; MODELEFFECTS INTERCEPT TRT AGE SEXC BASVAL ; RUN; ODS OUTPUT PARAMETERESTIMATES=POOLED_DIFFS; PROC MIANALYZE DATA = DIFFS ; MODELEFFECTS ESTIMATE; STDERR STDERR; RUN;</pre>

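### The SANDE co-primary ANCOVA uses only one of the two SANDE scores collected before randomization; adding the screening score is a cheap gain in precision of uncertain, possibly negligible, size

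*Protocol*

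**What the plan says.** The protocol's Schedule of Evaluations marks SANDE at screening and at every visit from Visit 1 to week 16. Protocol 6.1 lists "Assessment by SANDE questionnaire" among the procedures of both the screening visit and Visit 1. At Visit 1 it precedes the eligibility check and randomization. The two readings are separated by the wash-out: "The wash out period should not be less than 8 days and more than 10 days". SANDE is also an entry criterion ("SANDE questionnaire global score > 25 mm"), and eligibility is checked at both visits.

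The synopsis gives the method without naming covariates: "The change from baseline in SANDE global score at week 12 will be analyzed by means of an adjusted ANCOVA procedure". SAP 4.5 defines baseline as one visit, the last up to and including randomization. For the week 12 analysis, SAP 10.1.2.2 adjusts for "gender, age class, baseline global SANDE score as fixed effects and site as random effect". Protocol 9.4.3.1 names the same four factors without calling site random. The model line in SAP 15.5.2 is "MODEL AVAL=TRT AGE SEXC BASVAL /S", in which BASVAL is the only SANDE term. The imputation code there uses baseline and weeks 2, 4 and 8. SAP 10.2.2.2 and 10.2.2.3 carry the same approach over to SANDE severity and frequency at week 12 (key secondary endpoints 2 and 3).

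Neither document gives the screening score a role in these analyses or a reason for leaving it out.

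**The concern.** The global SANDE score is the square root of the product of two marks on 100 mm lines (SAP 12.2), so a single reading is likely to be a noisy measure of a patient's usual symptom level. A second reading taken before randomization may predict week 12 beyond the first. Because it precedes allocation, adjusting for it cannot bias the treatment comparison.

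Both co-primaries must be won, with about 45 evaluable patients per arm, and the planned joint power is 90% with no margin. Any variance the screening score could explain stays in the standard error of an endpoint on which the trial depends, although the data are already being collected.

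**Working it through.** **Inputs from SAP section 5.** Difference 15 points, SD 20, 90 evaluable patients at 1:1 (45 per arm), one-sided alpha 0.025. Stated power is 94.0% for SANDE, 95.8% for Schirmer and 90% overall.

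**Reproducing the plan.** The noncentrality is 15 / (20 × √(2/45)) = 3.558. A two-sample t-test on 88 degrees of freedom then has power 94.04%, against 94.0% stated. The joint figure is 0.958 × 0.940 = 0.9005, against 90%. The plan's figures stand.

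**Gain from the second score.** Let a be the screening-baseline correlation, b the baseline-week 12 correlation and c the screening-week 12 correlation. With the Visit 1 score alone, residual variance is proportional to 1 − b². Adding the screening score lowers it by the fraction

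(c − ab)² / [(1 − a²)(1 − b²)],

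the squared partial correlation of screening with week 12 given baseline. The documents give none of a, b or c, so every value below is assumed. SD 20 is taken as the current residual SD, and power allows for one fewer degree of freedom.

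*Case 1: readings 8-10 days apart correlate more strongly than readings 12 weeks apart.*

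| a / b / c | Variance reduction | SD | SANDE power |
|---|---|---|---|
| 0.7 / 0.5 / 0.5 | 5.9% | 19.40 | 95.2% |
| 0.8 / 0.5 / 0.5 | 3.7% | 19.63 | 94.8% |
| 0.7 / 0.5 / 0.45 | 2.6% | 19.74 | 94.6% |
| 0.7 / 0.5 / 0.4 | 0.7% | 19.93 | 94.2% |
| 0.8 / 0.6 / 0.5 | 0.2% | 19.98 | 94.1% |
| 0.7 / 0.5 / 0.35 | 0% | 20.00 | 94.0% |

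Worked example, third row: (0.45 − 0.35)² / (0.51 × 0.75) = 0.0100 / 0.3825 = 2.6%. In the last row c = ab, so the screening score adds nothing.

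A variant keeps a = b = r, with r from 0.4 to 0.7, and sets c = 0.8r because the screening score precedes wash-out. The reduction is then 2-4% and power 94.4-94.9%.

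*Case 2: one common correlation r among all three readings.* The variance ratio simplifies to (1 + 2r)/(1 + r)².

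| r | Variance reduction | SD | SANDE power |
|---|---|---|---|
| 0.4 | 8.2% | 19.17 | 95.7% |
| 0.5 | 11.1% | 18.86 | 96.2% |
| 0.6 | 14.1% | 18.54 | 96.7% |
| 0.7 | 17.0% | 18.23 | 97.1% |

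Joint power (× 0.958) moves from 90.1% to at most 91.2% in Case 1, and to 91.6-93.1% in Case 2.

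**Price of the extra term.** The planned model has five fixed parameters (intercept, treatment, gender, age class, baseline), which leaves about 90 − 5 = 85 degrees of freedom if the random site effect is ignored. A covariate that predicts nothing adds about 1/85 = 1.2% to the variance of the treatment difference through chance imbalance. The power figures above leave this out. It would cost about 0.2-0.3 of a power point, so a reduction below about 1% brings no net gain.

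**Meaning of SD 20.** The documents do not say whether it is a change-score SD or a residual SD. If it is a change-score SD and r = 0.5, the single-score residual SD is √(400 × 1.5/2) = 17.32, giving power 98.2%. With two scores it is 16.33, giving 99.1%. The relative variance reduction is unchanged, but the power gain is under one point.

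**The case against.** The strongest reply is that nothing is wrong. The ANCOVA is valid, names the same covariates in both documents, and adjusts for site, gender and age class as well as baseline. Its stated power reproduces. All of that stands.

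The screening score is also not a clean replicate. Exclusion criteria 12 and 13 allow topical corticosteroids, lifitegrast, autologous serum, contact lenses and punctum plugs up to screening and require them to stop there. The screening reading may therefore reflect each patient's earlier regimen, whereas Visit 1 follows wash-out. Selection at more than 25 mm restricts the range further. Preferring the post-wash-out score is defensible. This limits the likely gain, but it does not remove the case for using both scores.

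Imputation is a fair objection too. Step 2 of the primary imputation is fitted only on retrieved drop-outs. With about 100 patients and 10% assumed not evaluable, there may be very few. If that model does not converge, the SAP switches to Copy Reference. Another correlated predictor there could change the primary missing-data method. The fix must respect this, and it does.

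A reader might infer that a second reading is bound to predict week 12 beyond the first. The documents do not show that: they report no correlations, and plausible values take the contribution to zero.

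**Conclusion.** SANDE is collected twice before randomization and the co-primary model uses one of the two scores. Adding the other is unbiased and nearly free, so it is worth doing, but as an efficiency gain of modest priority and not as the correction of a fault.

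The more credible range is a 0-6% cut in residual variance, or about 0-1 point on the 94.0% power. It assumes that correlation weakens with time or that the pre-wash-out score predicts week 12 less well. The 8-17% cut, worth up to about 3 points, needs readings 8-10 days apart to correlate no more strongly than readings 12 weeks apart. A reader might turn that upper range into an equivalent of 9-20% more patients (1/0.918 to 1/0.830) and treat it as the expected benefit. The documents do not support this. Nor do they support calling the trial underpowered or the estimate biased for want of this covariate. All power figures take SD 20 as the residual SD.

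**What to change.** Before unblinding:

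- Add the screening (Day -8) global SANDE score as a second continuous covariate in the ANCOVA of SAP 10.1.2.2 and the PROC MIXED model of SAP 15.5.2.
- Add the screening severity and frequency scores in the same way for key secondary endpoints 2 and 3.
- Keep change from baseline defined against Visit 1, so the endpoint, estimand and hypotheses do not change.
- The screening score may also enter the step 1 MCMC imputation and the MAR sensitivity imputation. Do not add it to the step 2 retrieved drop-out regression.
- List the change in SAP 7.9 as a departure from the covariates named in protocol 9.4.3.1.

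The cost is one model term, one degree of freedom and a recorded departure from the protocol, with the risk that little is gained. No visit, patient or measurement is added.
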